5 TREATMENTS

5.1 Study treatment

Study treatments include the following doses of ACT-132577: 5 mg, 10 mg (2×5 mg), 25 mg, 50 mg, as well as placebo and lisinopril 20 mg. The ACT-132577 and its matching placebo will be provided as identical capsules of size "0".

Lisinopril 20 mg tablet, as active reference, is over-encapsulated (capsule size "0"). Matching placebo to lisinopril capsules will be provided as identical capsules of size "0", see Section 5.1.4.2.

5.1.1 Investigational treatment: description and rationale

Four fixed doses of ACT-132577 (5 mg, 10 mg [2 \times 5 mg], 25 mg, and 50 mg) covering a dose range of 10-fold are selected for the present dose finding study. The study treatment must be taken orally o.d. based on the PK profile of ACT-132577 ($t_{1/2}$ of approximately 44 h). ACT-132577 can be administered irrespective of food as the PK of ACT-132577 were not affected by food [ACT-132577 IB].

In the AC-080-101 Phase 1 study, a dose-dependent increase in ET-1 plasma concentrations was observed after several days of treatment up to the highest tested dose of 100 mg ACT-132577.

At a dose of 5 mg, ET-1 plasma concentrations did not differ from subjects treated with placebo, whereas 25 mg induced a clear increase in ET-1 plasma concentration. Therefore, 5 mg and 10 mg are selected to cover the lower-part of the dose-response curve. 25 mg and 50 mg are selected to complete the dose-response curve. The exposure margins and the nonclinical safety program support this Phase 2 clinical trial at doses up to 50 mg o.d. for a treatment period of 8 weeks [ACT-132577 IB].

Essential hypertension Protocol AC-080A201 Version 3 30 May 2016, page 43/112

Confidential

5.1.2 Comparator(s): description and rationale

The regulatory guidelines and scientific standards recommend use of a reference drug [ICH 2000a, ICH 2000b, EMA 2010].

Lisinopril is the active reference drug. An o.d. dose of 20 mg provides statistically and clinically significant decreases in SBP/DBP at trough after 6 weeks of treatment compared to placebo [Gomez 1989].

5.1.3 Placebo: description and rationale

Placebo is used as the control group in the DB period as recommended by health authorities [ICH 2000a, ICH 2000b, EMA 2010] for short-term studies (4–12 weeks).

The use of placebo is justified due to the following reasons:

- Only mild-to-moderate (grade 1 and 2) hypertensive subjects will be enrolled into this study.
- Subjects are closely followed throughout the study (8 to 9* visits at site).
- Study-specific discontinuation criteria have been set-up [see Section 5.1.12].
- No irreversible harm was reported during this short term period by an FDA meta-analysis of 590 individual hypertension clinical trials involving 64,438 subjects randomized to experimental drug and 21,699 randomized to placebo [DeFelice 2008].

Placebo matching ACT-132577 and placebo matching lisinopril capsules will be concomitantly administered orally o.d. during the SB placebo run-in and SB placebo withdrawal periods to all subjects and during the double-blind treatment period to those subjects who have been randomized to the placebo group.

5.1.4 Study treatment administration

Study treatment is supplied in bottles containing 36 capsules to provide 36 days of treatment to cover a 4-week treatment period and the time window to the next visit.

Study treatment consists of 2 bottles. The subjects must be instructed to take one capsule from each bottle (i.e., total of 2 capsules) orally o.d. irrespective of food intake every morning between 7:00 and 10:00 a.m., and not to take it on the morning of study visit days.

See Table 1 and Section 8 for details on study treatment dispensing.

^{*} Nine visits: Only for women of childbearing potential.

Essential hypertension Protocol AC-080A201 Version 3 30 May 2016, page 44/112

Confidential

5.1.4.1 Run-in period (single-blind placebo)

Subjects will receive 2 bottles; one bottle contains placebo capsules matching ACT-132577 and the other bottle contains placebo capsules matching lisinopril. The subjects must be instructed to take one capsule from each bottle (i.e., total of 2 capsules) o.d. every morning from the morning of the Screening visit (Visit 1) to the morning of Visit 4 / Pre-randomization (Day -1). The run-in period is an SB period (subject-blinded). Accordingly, site staff must not inform the subject of the treatment received during this period.

5.1.4.2 Double-blind treatment period

All subjects will receive 2 bottles and must be instructed to take one capsule from each bottle (i.e., total of 2 capsules) o.d. every morning from the morning of Visit 4 / Randomization (i.e., Day 1, after completion of the baseline 24-h ABPM recording) to the morning of Visit 7 / Part 1. Depending on the DB study treatment arm the study treatment consists of:

- ACT-132577 5 mg: One bottle of ACT-132577 5 mg capsules + one bottle of placebo capsules matching lisinopril.
- ACT-132577 10 mg: Two bottles of ACT-132577 5 mg capsules.
- ACT-132577 25 mg: One bottle of ACT-132577 25 mg capsules + one bottle of placebo capsules matching lisinopril.
- ACT-132577 50 mg: One bottle of ACT-132577 50 mg capsules + one bottle of placebo capsules matching lisinopril.
- Lisinopril 20 mg: One bottle of lisinopril 20 mg capsules + one bottle of placebo capsules matching ACT-132577.
- Placebo: One bottle of placebo capsules matching ACT-132577 + one of placebo capsules matching lisinopril.

5.1.4.3 Withdrawal period (single-blind placebo)

All subjects will receive 2 bottles; one bottle contains placebo capsules matching ACT-132577 and the other bottle contains placebo capsules matching lisinopril. The subjects must be instructed to take one capsule from each bottle (i.e., total of 2 capsules) o.d. every morning from the morning of Visit 7 / Part 2 (i.e., after completion of the DB-EOT 24-h ABPM recording) to the morning of the day before Visit 8 (i.e., the WD-EOT visit). The WD period is an SB period (subject-blinded). Accordingly, site staff must not inform the subject of the treatment received during this period.

Essential hypertension Protocol AC-080A201 Version 3 30 May 2016, page 45/112

Confidential

5.1.5 Treatment assignment

After informed consent has been signed, the investigator/delegate contacts the Interactive Response Technology system (IRT) at Visit 1 (Screening visit) to get a subject number. After having confirmed the eligibility of the subject, the investigator/delegate contacts the IRT to receive the bottle numbers for the SB placebo run-in period.

For subjects on anti-hypertensive treatment, the investigator/delegate re-contacts the IRT at Visit 2 (Week -4) to get a new study treatment number (i.e., bottle numbers) for the remaining 4 weeks of the SB placebo run-in period. See Section 8 for more details.

At the end of the run-in period, after having confirmed the eligibility of the subject and prior to the start of DB treatment period, the investigator/delegate contacts the IRT at Visit 4 / Randomization (Day 1) to randomize the subject. The IRT assigns a randomization number to the subject and bottle numbers to match the treatment arm assigned by the randomization list. Randomization will be in a 1:1:1:1:1 ratio (ACT-132577 5 mg; ACT-132577 10 mg; ACT-132577 25 mg; ACT-132577 50 mg; lisinopril 20 mg; placebo). At Visit 6 (Week 4), the investigator/delegate re-contacts the IRT to get a new study treatment number (i.e., bottle numbers) for the remaining 4 weeks of the DB treatment period. See Section 8 for more details.

At the end of the DB treatment period (Visit 7), the investigator/delegate contacts the IRT to get the study treatment number (i.e., bottle numbers) for the SB placebo withdrawal period.

The randomization list is generated by an independent Contract Research Organization (CRO), using SAS version 9.3.

5.1.6 Blinding

This study will have an SB placebo run-in period prior to randomization. After randomization, the study will be performed in a DB fashion. This is followed by an SB placebo withdrawal period. During the placebo run-in and placebo WD periods, only the subject will be blinded to the treatment.

The investigator and study staff, the subjects, the monitors, Actelion staff, and CROs involved in the conduct of the study will remain blinded to the study treatment during the double-blind treatment period and until study closure. Actelion staff responsible for clinical trial supply distribution will need to be unblinded to ensure adequate distribution of study treatment. These persons will be clearly identified, their unblinding will be documented in the trial master file and they will not take part in any Clinical Trial Team meetings after study set-up has been completed.

Essential hypertension Protocol AC-080A201 Version 3 30 May 2016, page 46/112

Confidential

Until the time of unblinding for final data analysis, the randomization list is kept strictly confidential and accessible only to authorized persons, (i.e., Global Quality Management, IRT provider), who are not involved in the conduct of the study.

The investigational treatment, active reference and the respective matching placebos are indistinguishable and all study treatments will be packaged in the same way.

5.1.7 Unblinding

5.1.7.1 Unblinding for final analyses

Full randomization information will be made available for data analysis only after database closure in accordance with Actelion standard operating procedures (SOPs).

5.1.7.2 Unblinding for SUSARs

When a suspected unexpected serious adverse reaction (SUSAR) occurs for a subject participating in the study, Actelion Global Drug Safety will request the unblinding of the treatment assignment. The randomization code will not be communicated to the site staff or to the Actelion study team; unblinded SUSAR information will be anonymized and provided to Actelion Global Drug Safety, respective health authorities and Institutional Review Boards / Independent Ethics Committees (IRBs/IECs) only. SUSARs will be reported to investigators in a blinded fashion.

5.1.7.3 Emergency procedure for unblinding

The investigator, study staff and sponsor staff must remain blinded to the subject's study treatment assignment. The identity of the study treatment may be revealed only if the subject experiences a medical event, the management of which would require knowledge of the blinded treatment assignment. In this case, the investigator can receive the unblinded randomization code for study treatment allocation through the IRT. In these situations, the decision to unblind resides solely with the investigator. Whenever it is possible and if it does not interfere with (or does not delay) any decision in the best interest of the subject, the investigator is invited to discuss the intended unblinding with Actelion.

The occurrence of any unblinding during the study must be clearly justified and explained by the investigator. In all cases, Actelion must be informed as soon as possible before or after the unblinding.

The circumstances leading to unblinding must be documented in the Investigator Site File (ISF) and eCRF.

Essential hypertension Protocol AC-080A201 Version 3 30 May 2016, page 47/112

Confidential

5.1.8 Study treatment supply

Manufacturing, labeling, packaging, and supply of study treatment will be conducted according to Good Manufacturing Practice, Good Clinical Practice (GCP), and any local or national regulatory requirements.

All study treatment supplies are to be used only in accordance with this protocol, and not for any other purpose.

5.1.8.1 Study treatment packaging and labeling

5.1.8.1.1 Study treatment packaging

Study treatment is provided as capsules and supplied in childproof bottles for all periods.

5.1.8.1.2 Study treatment labeling

Study treatment is labeled to comply with the applicable laws and regulations of the countries in which the study sites are located.

5.1.8.2 Study treatment distribution and storage

Study treatment supplies must be kept in an appropriate, secure area and stored according to the conditions specified on the label.

5.1.8.3 Study treatment dispensing

The subjects will receive sufficient study treatment to cover the period up to the next scheduled visit. Subjects are asked to return all used, partially used, and unused study treatment bottles at each visit. The protocol-mandated study treatment dispensing/return procedures may not be altered without prior written approval from Actelion. An accurate record of the date and amount of study treatment dispensed to and returned from each subject must be available for inspection at any time.

5.1.8.4 Study treatment return and destruction

On an ongoing basis and/or on termination of the study, the monitor will collect used and unused subject bottles, which will be sent to the warehouse, where Actelion or a deputy will check treatment reconciliation. In certain circumstances, used and unused study treatment containers may be destroyed at the site once study treatment accountability is finalized and has been checked by Actelion or the deputy, and written permission for destruction has been obtained from Actelion.

5.1.9 Study treatment accountability and compliance with study treatment

5.1.9.1 Study treatment accountability

The inventory of study treatment dispensed and returned (i.e., study treatment accountability) must be performed by the study staff on the day of the subject visit and before providing further study treatment. It is recorded on the Investigational Medicinal

Essential hypertension Protocol AC-080A201 Version 3 30 May 2016, page 48/112

Confidential

Product dispensing and accountability log and in the eCRF and checked by the monitor during site visits and at the end of the study. The study treatment accountability log in the eCRF will include at least the following information for each study treatment unit (bottle) dispensed to the subject:

- Dispensed bottle numbers
- Date dispensed / Number of capsules dispensed
- Date returned / Number of capsules returned

All study treatment supplies, including partially used or empty bottles must be retained at the site for review by the monitor.

If the subject forgets to bring the remaining study treatment to a study visit, he/she must be instructed to bring it at the next visit.

5.1.9.2 Study treatment compliance

Study treatment compliance is based on study treatment accountability. Study treatment compliance will be calculated by site for each study visit and period using the formula defined below:

Compliance = [(number of capsules* dispensed – number of capsules* returned) / Total number of capsules* that should have been taken during a period] × 100

At the end of the run-in period, eligibility with regard to study treatment compliance during run-in period [see Section 4.3] will be assessed as follows: Subject is considered compliant and therefore is eligible for randomization if accountability-based compliance is $\geq 80\%$. In order to minimize misuse of study medication by the subject (e.g., throwing out capsules from the returned bottles) and to properly evaluate this inclusion criterion, the study staff must not inform the subject about this criterion.

After randomization, compliance is still expected to be between 80% and 120%. If out of range value(s) are noticed (from study treatment accountability), they will be considered as a protocol deviation. The investigator must check with the subject the reasons for this non-compliance and discuss actions to be taken to avoid re-occurrence at the next visit.

5.1.10 Study treatment dose adjustments and interruptions

Study treatment dose adjustments are not permitted.

Study treatment may be temporarily interrupted in response to an AE, a diagnostic or therapeutic procedure, a laboratory abnormality, or for administrative reasons. Study-specific criteria for interruption of study treatment are described in Section 5.1.12.

^{*} From both bottles

Essential hypertension Protocol AC-080A201 Version 3 30 May 2016, page 49/112

Confidential

If study treatment intake is interrupted by the subject for any reason, she/he must immediately inform the investigator.

Interruptions of study treatment should be kept as short as possible. If treatment is stopped for more than 4 consecutive days, re-introduction is not permitted and treatment must be permanently discontinued [see Section 5.1.12].

Study treatment interruptions must be recorded in the eCRF.

5.1.11 Premature discontinuation of study treatment

The decision to prematurely discontinue study treatment may be made by the subject, the investigator, or Actelion. The main reason and whether discontinuation of study treatment is the decision of the subject, the investigator, or Actelion must be documented in the eCRF.

A subject has the right to prematurely discontinue study treatment at any time by withdrawal from study treatment only or by withdrawal from any further participation in the study (i.e., premature withdrawal from the study, see Section 9.2).

The investigator should discontinue study treatment for a given subject if, on balance, he/she believes that continued administration would be contrary to the best interests of the subject.

Study treatment may be discontinued in response to an AE, lack of efficacy (including treatment failure, worsening of subject's condition), a protocol deviation (including eligibility failure, non-compliance with study requirements), a diagnostic or therapeutic procedure, or for administrative reasons.

Study-specific criteria for discontinuation of study treatment are described in Section 5.1.12.

A subject who prematurely discontinues study treatment is NOT considered withdrawn from the study and will be asked to return for a premature EOT visit (Visit 9) within 7 days of last intake of study treatment and thereafter might be contacted for the safety follow-up telephone call or follow-up visit [see Sections 8.4 and 8.5], provided that the subject's consent for this limited participation in the study has not been withdrawn.

A subject who prematurely discontinues study treatment and withdraws consent to participate in any further study assessments is considered withdrawn from the study. Subjects who die or are lost to follow-up are also considered withdrawn from the study. Withdrawal from the study and follow-up medical care of subjects withdrawn from the study is described in Sections 9.2 and 9.4, respectively.

Essential hypertension Protocol AC-080A201 Version 3 30 May 2016, page 50/112

Confidential

5.1.12 Study-specific criteria for interruption / premature discontinuation of study treatment

A) Hypertension

At any time throughout the study if mean SiDBP \geq 110 mmHg and/or mean SiSBP \geq 180 mmHg is measured by OBPM, i.e., essential hypertension grade 3 [Mancia 2013], BP must be re-measured. If the value (i.e., mean SiSBP \geq and/or DBP \geq 110 mmHg measured by OBPM at the site) is confirmed, subject must permanently discontinue study treatment.

The BP re-measurement can be during the same visit (e.g., within 1 h), or at the next planned visit, or at an unscheduled visit. The time of re-measurement is at investigator's discretion, taking into consideration the subject's medical history.

B) Pregnancy

If a female subject becomes pregnant while on study treatment, study treatment must be discontinued immediately, and a Pregnancy Form must be completed [see Section 10.3].

C) Liver aminotransferases abnormalities

Interruption of study treatment

After randomization study treatment must be interrupted in the following cases:

• Aminotransferases (i.e., ALT and/or AST) ≥ 3 and $\leq 8 \times ULN$

Perform a re-test of aminotransferases (ALT and AST), total and direct bilirubin, and alkaline phosphatase within 48 h. If AST and/or ALT elevation is confirmed, the re-introduction of study treatment is not to be considered.

Interruptions must be for less than 5 consecutive days; longer interruptions must lead to permanent discontinuation of study treatment [see Section 5.1.10].

Aminotransferases, total and direct bilirubin, and alkaline phosphatase levels must be monitored weekly after study drug discontinuation until values return to pre-treatment levels or within normal ranges.

Permanent discontinuation of study treatment

Study treatment must be stopped and its re-introduction is not to be considered in the following cases:

- Aminotransferases > 8 × ULN.
- Aminotransferases ≥ 3 × ULN and associated clinical symptoms of liver injury, e.g., nausea, vomiting, fever, abdominal pain, jaundice, unusual lethargy or fatigue, flu like syndrome (arthralgia, myalgia, fever).

Essential hypertension Protocol AC-080A201 Version 3 30 May 2016, page 51/112

Confidential

• Aminotransferases $\geq 3 \times \text{ULN}$ and associated increase in total bilirubin $\geq 2 \times \text{ULN}$.

Aminotransferases, total and direct bilirubin, and alkaline phosphatase levels must be monitored weekly after study drug discontinuation until values return to pre-treatment levels or within normal ranges.

Other diagnoses (e.g., viral hepatitis, mononucleosis, toxoplasmosis, cytomegalovirus) and/or etiologies (e.g., acetaminophen-related liver toxicity) should be considered and ruled out by performing the appropriate tests.

All liver aminotransferases abnormalities leading to study drug interruption or discontinuation must be recorded as AEs [see Section 10].

An ILSDRB provides ongoing assessment and advice regarding any hepatic events that may require further evaluation during the study.

To ensure the proper and comprehensive evaluation of hepatic events, additional subject data might be collected via Actelion Global Drug Safety.

D) Hemoglobin abnormalities

In the event of hemoglobin decrease from baseline* of > 20 g/L, a hemoglobin retest must be performed within 10 days, with additional laboratory evaluations that may include, but are not limited to, any of the following:

 Red blood cell cellular indices (mean corpuscular volume, mean corpuscular hemoglobin, mean corpuscular hemoglobin concentration), peripheral blood smear, reticulocyte count, iron status (iron level, serum ferritin, total iron binding capacity, transferrin saturation), lactate dehydrogenase (LDH), indirect bilirubin.

Study drug should be stopped if clinically mandated based on the investigator's judgment, or in any of the following situations:

- A decrease in hemoglobin to < 80 g/L (< 4.9 mmol/L),
- A decrease in hemoglobin from baseline of > 50 g/L,
- The need for transfusion.

E) Initiation of forbidden medications

Study treatment must be permanently discontinued if any forbidden therapy as listed in Section 5.2.4 is started during the study.

^{*} Baseline hemoglobin: last value obtained prior to first intake of DB study treatment.

Essential hypertension Protocol AC-080A201 Version 3 30 May 2016, page 52/112

Confidential

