	 Treatment-emergent marked laboratory abnormalities; Changes from baseline to Weeks 2, 4 and 8 of DB treatment period (Period II) in laboratory parameters; Changes from baseline to Weeks 4 and 8 of DB treatment period (Period II) in ECG parameters (PR, QRS, QT, QTcB, QTcF); Changes from baseline to Weeks 2, 4 and 8 of DB treatment period (Period II) in body weight and heart rate. See Section 10.1.1 for definition of 'treatment-emergent'. Pharmacokinetic/pharmacodynamic endpoints Pharmacokinetic / pharmacodynamic endpoints are described in Section 6.2. 					
ASSESSMENTS	in Section 6.3. Refer to the schedule of assessments in Table 1.					
STATISTICAL METHODOLOGY	The Full Analysis Set (FAS) includes all subjects randomized to a study treatment, who have a baseline mean trough SiDBP.					
	The Per-Protocol Set (PPS) includes all subjects from the FAS who have a mean trough SiDBP at Week 8 of DB treatment period (Period II) and do not have any major protocol deviation. Major protocol deviations will be described in the Statistical Analysis Plan.					
	The Safety Set includes all subjects who received at least one dose of study treatment in DB treatment period (Period II).					
	Statistical hypotheses The null hypothesis to be tested is that there is no dose-response for the primary endpoint.					
	H_0 : $\mu_0 = \mu_1 = \mu_2 = \mu_3 = \mu_4$					
	Here, μ_i denotes the mean change from baseline to Week 8 in mean trough SiDBP (μ) for ACT-132577 dose (i) (where $i=0$ corresponds to placebo). A value of $\mu_i < 0$ corresponds to a decrease in SiDBP.					
	The alternative hypothesis is that there is a monotonic dose-response for the primary endpoint.					
	H ₁ : $\mu_0 \ge \mu_1 \ge \mu_2 \ge \mu_3 \ge \mu_4$ and $\mu_i > \mu_j$ for at least one $i > j$ or $\mu_0 \le \mu_1 \le \mu_2 \le \mu_3 \le \mu_4$ and $\mu_i < \mu_j$ for at least one $i > j$					

Note that larger values of μ_i –corresponding to less decrease (or more increase) from baseline to Week 8 in mean trough SiDBP with increasing dose of ACT-132577– are less favorable. The first part of the alternative hypothesis corresponds to ACT-132577 being superior to placebo.

Type I and II errors and power

The type I error (α) is set to 0.05 (two-sided). The type II error is set to 0.10 and therefore the power to 90%.

Primary analysis

The primary analysis will be conducted on the PPS.

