Change from baseline to Week 8 in mean trough office SiDBP will be analyzed using the MCP-Mod approach. In brief, it consists of a set of Multiple Contrast Tests (MCTs) to establish the existence of a dose-response and a set of pre-specified dose-response models to describe the dose-response curve.

Six candidate dose-response models will be considered: linear, linear in log-dose, quadratic, E_{max} , sigmoidal E_{max} and logistic. The analysis will be performed using the R-package DoseFinding. A dose-response relationship is demonstrated if at least one of the six MCTs has an adjusted p-value < 0.05.

Supportive and sensitivity analyses will be conducted on the PPS and FAS. Change from baseline to Week 8 of DB treatment period (Period II) in mean trough SiDBP (imputed by last observation carried forward, if applicable) will also be analyzed using an analysis of covariance model with a factor for treatment group (placebo and four doses of ACT-132577) and a covariate for baseline mean trough SiDBP. Each of the four doses of ACT-132577 will be compared to placebo applying the Dunnett's test.

Secondary analyses

Secondary efficacy variables will be analyzed for the PPS at $\alpha = 0.05$ (two-sided) using 95% confidence intervals (CIs). No correction for multiple testing will be applied for these analyses.

Safety analyses

Safety analyses will be performed on the Safety Set. Safety data will be summarized using descriptive statistics.

Interim analysis

No formal interim analysis is planned.

Sample size

In a previous study with macitentan in essential hypertension (AC-055-201) the within-group standard deviation (SD) for the change from baseline to Week 8 in SiDBP was 7.4 mmHg (90% CI: 7.0–8.0).

It is assumed that the maximum difference versus placebo is achieved at the highest dose of ACT-132577.

For the sample size it was required that the power to demonstrate the existence of a dose-response relationship — conservatively assuming a maximum difference versus placebo of 4 mmHg and an SD = 9 mmHg — is 90%. A total of 70 subjects per group in the PPS (i.e., 420 subjects in total) satisfied this condition and would also allow for sufficiently precise estimation of the dose-response curve. Assuming a drop-out rate of approximately 20%, a total of 90 patients per group would need to be randomized (i.e., 540 in total).

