6 STUDY ENDPOINTS

6.1 Efficacy endpoints

6.1.1 Primary efficacy endpoint(s)

The primary efficacy endpoint is the change from baseline to Week 8 of DB treatment period (Period II) in mean trough (i.e., 24 h post-dose) SiDBP, measured by OBPM.

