8.6 Unscheduled visits

Unscheduled visits may be performed at any time during the study. Depending on the reason for the unscheduled visit (e.g., loss of efficacy, AE, etc.), appropriate assessments [as specified in Table 1] may be performed based on the judgment of the investigator and must be recorded in the eCRF. After an unscheduled visit, the regular scheduled study visits must continue according to the planned visit and assessment schedule.

Essential hypertension Protocol AC-080A201 Version 3 30 May 2016, page 75/112

Confidential

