All assessments (including the unscheduled ones) are considered and re-assigned to the most appropriate visit according to the time windows described in Section 11; reference to visits are to be intended as references to re-mapped visit, i.e., time window visits.

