11 GENERAL DEFINITIONS AND DERIVATIONS

11.1 Time windows

To allow analysis of data at the relevant planned (scheduled) visits, all recorded assessments, including unscheduled ones, are re-assigned to the most appropriate visit according to the best fitting time window for that visit [see Table 5]. Note that there are no 'gaps' between the visit windows in order to keep all values in the analysis.

Table 5 Visit time windows

Visit	Target day*	Min. day	Max. day
1	-42	-	-35
2	-28	-34	-18
3	-7	-17	-4
4	1	-3	1
5	14	1	21
6	28	22	42
7 - I	55	43	EOT***
7 - II**	56	EOT + 01 m	EOT + 25 h
8	70	EOT + 25 h 01 m	No limit

* Number of days from start of double-blind treatment.

** Only for ABPM.

*** For OBPM use EOT + 05 m (for the time of the average SiDBP)

ABPM = ambulatory blood pressure monitoring; EOT = End-of-Treatment; OBPM = office blood pressure measurement; SiDBP = sitting diastolic blood pressure.

For assessments for which time is collected, please use the following rules:

- Target day = Target day and time 12:00
- Min. day = Min. day and time 0:00
- Max. day = Max. day and time 23:59

Visit 4 / Day 1

- Target day 1 = Start date/time of DB treatment
- Max. day1 = Start date/time of DB treatment

Visit 5 / Day 1

- Min. day 1 = Start date/time of DB treatment + 1 minute

Visit 7 - I / EOT

- Max. day = End date/time of DB treatment

Visit 7 - II / EOT

- Min. day = End date/time of DB treatment + 1 minute

In the event that there is more than one value within the same time window, the value closest to the planned assessment date will be taken. In the event of equidistant values from the planned time point, the last assessment will be considered for the analyses. Where multiple assessments fall on the same day the latest is then used.

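### SAP 5.5 and 11.1 give the scheduled trough reading no priority, so a repeat prompted by a high value, or a nearer unscheduled reading, can become the Week 8 endpoint

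*Protocol*

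**What the plan says.** **Endpoint.** Protocol 6.1.1 defines the primary endpoint on "mean trough (i.e., 24 h post-dose) SiDBP, measured by OBPM". SAP 5.5.1 retrieves it by test code and the 'Average' category. It has no filter for scheduled, first or pre-dose readings.

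**Repeats.** Protocol 5.1.12 A requires re-measurement after a grade 3 value and states: "The BP re-measurement can be during the same visit (e.g., within 1 h), or at the next planned visit, or at an unscheduled visit". The timing is left to the investigator. Protocol 7.2.1, by contrast, requires blood pressure in general to be taken at trough, before study drug.

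**Unscheduled visits.** Protocol 8.6: "Unscheduled visits may be performed at any time during the study". It names loss of efficacy and adverse events as example reasons and sets no trough condition of its own.

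**Selection rule.** SAP 5.5: "All assessments (including the unscheduled ones) are considered and re-assigned to the most appropriate visit according to the time windows described in Section 11". When several readings share a window, SAP 11.1 says "the value closest to the planned assessment date will be taken", and adds: "Where multiple assessments fall on the same day the latest is then used". For office readings the Visit 7 window closes 5 minutes after the last double-blind intake. The Visit 5 and Visit 6 windows have no limit tied to the dose.

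**The concern.** Together these rules let the value of the outcome decide which reading is analysed. Only a high first reading earns a second one, and the second then overrides the first. A reading selected for being high tends to be followed by a lower one. If the drug works, placebo and low-dose subjects cross the trigger more often, so more of their high values are replaced downward and the contrast with placebo shrinks.

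A second route is displacement by date. An unscheduled reading prompted by symptoms or loss of efficacy can be nearer to Day 55 than the scheduled Visit 7 and take its place.

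A third affects Weeks 2 and 4. Dosing is on site at Visits 5 and 6, so a repeat within the hour could follow the dose and still be used as the latest of the day. Those values feed the LOCF, mixed-model and average-over-time analyses.

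The result at stake is the dose-response estimate and the minimum effective dose, which SAP 10.6.3 sets at a 4 mmHg placebo-corrected reduction. None of the supportive and sensitivity analyses in SAP 10.6.4 or SAP Table 4 is restricted to scheduled trough readings.

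**Working it through.** **1. The plan's own figure.** The synopsis plans by "conservatively assuming a maximum difference versus placebo of 4 mmHg and an SD = 9 mmHg". Protocol Table 4 gives 63 per group (378 in total) for 90% average power at SD 9. Re-implementing the R code in the re-estimation SAP (six optimal contrasts, two-sided test at 0.05, critical value 2.16, four sigmoid Emax curves) gives 62 per group (372), and 90.5% average power at 63. Table 4 therefore reproduces, and the same code can price a loss of effect.

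**2. Bias from a same-day pre-dose repeat.** Let the first Week 8 reading be normal with mean m and SD s, let the repeat correlate r with it, and let the repeat be used when the first is 110 or more. With z = (110 − m)/s and φ the normal density:

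- share re-measured = P(Z > z)
- downward shift in the arm mean = (1 − r) × s × φ(z)
- loss of contrast = placebo shift − active shift

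Assumed, because the documents do not give them: s = 9.5, baseline mean 96 to 100, r = 0.7 to 0.9, change −4 on placebo and −8.5 on active. The −4 and the range −8 to −9 stand in SAP 10.6.3.

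Baseline 98, r = 0.8:

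- Placebo: m = 94, z = 16/9.5 = 1.684, φ = 0.0966. Share 4.6%; shift 0.2 × 9.5 × 0.0966 = 0.184.
- Active: m = 89.5, z = 20.5/9.5 = 2.158, φ = 0.0389. Share 1.5%; shift 0.2 × 9.5 × 0.0389 = 0.074.
- Loss = 0.184 − 0.074 = 0.11 mmHg, so 4.5 becomes 4.39.

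Range: baseline 96 with r = 0.9 gives 0.04; baseline 100 with r = 0.7 gives 0.21.

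**3. Other assumptions (simulation).**

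| Assumptions | Triggered, placebo | Loss (mmHg) |
|---|---|---|
| Step 2 | 3–7% | 0.04–0.21 |
| Baseline mean 95–103, truncated to 90–110; SD of change 7.4 or 9; reading error SD 4 or 6; effect 4 | 2–12% | 0.06–0.36 |
| Baseline mean 95–100, truncated to 90–110; SD of change 7.4–9; reading error SD 3–5; subjects confirmed at 110 or more earlier removed | 0.5–4% | 0.02–0.17 |

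Every set assumes that each trigger is repeated the same day before the dose. The systolic trigger is not modelled in the second set and plays no part in step 2.

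**4. Effect on power.** A loss of 0.06 to 0.36 on 4 mmHg is 1.5% to 9%. Scaling all four curves by 0.985 and 0.91 at SD 9 moves average power at 63 per group from 90.5% to 89.7% and 84.9%, and at 70 per group from 93.0% to 92.3% and 88.2%.

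**5. Displacement by date.** Protocol 8.2.4.1 allows Visit 7 on Day 55 ± 5. SAP 11.1 sets the target at 12:00 on Day 55. A reading at 08:00 on Day 60 is 4 days 20 h = 4.83 days away. An 08:00 reading on Day 51 is 4.17 days away, and one on Day 50 is 5.17. Readings at that hour on Days 51 to 59 are therefore all nearer and would be used instead. If a share p of Week 8 values is replaced and the contrast among them falls by b, the effect becomes 4 − p × b. With p from 1% to 20% and b from −4 to +4, this runs from 3.2 to 4.8 mmHg, so no direction can be claimed.

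**The case against.** **Trough.** A reader might infer that repeats need not be at trough. The documents do not support that: Protocol 7.2.1 states the trough rule without exception, and 5.1.12 A leaves the timing open without waiving it. What stands is that the two passages must be reconciled.

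**Post-dose values in the primary endpoint.** A reader might also infer that post-dose repeats contaminate Week 8. The limit of 5 minutes after the last dose keeps same-day post-dose repeats at Visit 7 out. The gap is at Visits 5 and 6, whose values do not enter the primary observed-case PPS analysis; SAP 10.1 calls all the other analyses exploratory.

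**Direction.** It is tempting to say that the whole arrangement shrinks the dose effect. Only threshold-triggered repeats have a predictable direction. Post-dose readings on active drug would tend to enlarge the effect, and unscheduled readings could do either.

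**Size.** At SD 9 and 70 per group, the standard error of a pairwise difference is 9 × √(2/70) = 1.52 mmHg, so a loss of 0.04 to 0.21 is 3% to 14% of one standard error. Being toward zero, this route does not manufacture a dose-response. The repeat may also wait until the next planned visit, which after Visit 7 is Visit 8 and displaces nothing. Displacement by date needs a late Visit 7 and an office reading at an unscheduled visit, where assessments are optional. Home readings are not recorded in the eCRF.

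These points limit size and scope. That the rule is pre-specified and identical in every arm does not remove the problem, because the trigger depends on the outcome, which treatment changes.

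**Conclusion.** The selection rule in SAP 5.5 and 11.1 lets a reading taken because the scheduled one was high supply the primary endpoint, and no planned analysis would show how much this matters. For pre-dose same-visit repeats the bias is toward zero and modest: about 0.02 to 0.4 mmHg across three sets of assumptions, with average power at 63 per group near 90% at best and 85% at worst. That rests on assumed baseline means, variances and repeat correlations, and on every trigger being repeated the same day; the documents report no repeat rate.

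For unscheduled readings displacing a late Visit 7, neither direction nor frequency can be stated. For Weeks 2 and 4, a post-dose repeat can be used, with consequences confined to the supportive, sensitivity and average-over-time analyses. A general claim that non-trough readings replace the scheduled ones and shrink the effect goes further than the text allows.

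The point deserves action because the bias is avoidable and the remedy is cheap.

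**What to change.** In SAP 5.5 and 11.1, for the post-baseline office blood pressure efficacy windows:

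- Use the first pre-dose 'Average' recorded at the scheduled visit.
- Use a repeat or unscheduled reading only if the scheduled one is missing and the substitute was taken pre-dose and on treatment.
- List all other repeat and unscheduled readings.
- Report the present nearest-then-latest rule as a sensitivity analysis.

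Reconcile Protocol 5.1.12 A (investigator's choice of re-measurement time), Protocol 7.2.1 (general trough rule) and SAP 11.1 (which reading counts).

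The cost is SAP wording and one programming flag for scheduled, first of day and pre-dose. No new data are needed, and the stopping rule is unchanged.
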